4.2 Exclusion Criteria

- Patients may not be receiving any other investigational agents.
- No prior use of anthracyclines and taxanes for metastatic disease or in the adjuvant or

neoadjuvant setting.

- Metastatic lesions identifiable only by PET.
- QTc > 470 msec. Excluded are patients who may develop prolongation of QTc. These conditions include patients with hypokalemia or hypomagnesemia, patients with congenital long QT syndrome, patients taking anti-arrhythmic medicines or other medicinal products that lead to QT prolongation, and cumulative high-dose anthracycline therapy.
- Patients may not be receiving concurrent chemotherapy for treatment of metastatic disease.
- Active brain metastases: evidence of progression \leq 3 months after local therapy (patients should be asymptomatic and off corticosteroids and anticonvulsants for at least 3 months prior to study entry).
- Patients with brain metastases must have at least one site of measurable disease outside of the central nervous system.
- Uncontrolled concurrent illness including, but not limited to, ongoing or active infection, history of recent myocardial infarction, symptomatic congestive heart failure, unstable angina pectoris, cardiac arrhythmia, interstitial lung disease or psychiatric illness/social situations that would limit compliance with study requirements.
- Uncontrolled seizure disorder.
- Pregnant or lactating women are excluded. Because there is an unknown but potential risk for adverse events in nursing infants secondary to treatment of the mother, breastfeeding should be discontinued if the mother is treated. These potential risks may also apply to other agents used in this study.
- A prior invasive malignant disease within five years except for skin cancer (squamous cell or basal cell carcinoma).
- Patients with known history of HIV or Hepatitis B because of potential for added toxicity from treatment regimen.
- Dementia or altered mental status that would prohibit the understanding of informed consent.

4.3 Withdrawal of Patients

A patient should be withdrawn from the trial treatment if, in the opinion of the investigator, it is medically necessary, or if it is the wish of the patient. If a patient does not return for a scheduled visit, every effort should be made to contact the patient. In any circumstance, every effort should be made to document patient outcome. Patients should be removed from therapy if any of the following occurs:

- Disease progression in patients receiving the combination of Lapatinib and Veliparib. Every effort should be made to document objective evidence of tumor progression radiographically and not solely based on clinical and/or tumor marker suggestions of progression.
- The occurrence of unacceptable toxicity indicating the need for cessation of treatment. Patients will be followed until stabilization or resolution of the toxicity.
- The physician feels it is in the best interest of the patient to stop treatment.
- Patient refusal to continue with therapy.
- Non-compliance by the patient with protocol requirements.
- Patient is lost to follow-up. If a patient does not return for scheduled visits, every effort should be made to re-establish contact. In any circumstance, every effort should be made to document patient outcome, if possible.
- Patient becomes pregnant.
- Termination of the study by investigator industry partners.

Treatment may be delayed for up to 2 weeks beyond planned resumption of the next cycle. If a patient does not fulfill re-treatment criteria by that time, they will be removed from the trial; if unacceptable toxicity to one of the agents used in this combination occurs in a patient enrolled in the study, then patient will NOT continue on a single agent.

4.4 Pregnancy

Prior to study enrollment, women of childbearing potential must be advised of the importance of avoiding pregnancy during trial participation, the potential risks of an unintentional pregnancy and should practice an effective method of birth control. Women of childbearing potential must have a negative pregnancy test within 7 days of initial dosing. The minimum sensitivity of the pregnancy test must be 25 IU/L or equivalent units of HCG. If the pregnancy test is positive, the patient must not receive investigational product and must not be enrolled in the study. In addition, all women of childbearing potential must be instructed to contact the Investigator immediately if they suspect they might be pregnant (e.g., missed or late menstrual period) at any time during study participation. The Investigator must immediately notify our industry partners (AbbVie and Novartis Pharmaceuticals Corporation) in the event of a confirmed pregnancy in a patient participating in the study.

5.0 DRUG INFORMATION

5.1 Veliparib or ABT-888

Veliparib is an oral potent inhibitor of PARP which is a nuclear enzyme that recognizes DNA damage and facilitates DNA repair. PARP activity is essential for the repair of single-stranded DNA breaks through the base-excision repair pathways and is important modulator of the non-homologous end-joining and homologous recombination double-stranded break repair pathways. The patient's weight will NOT be used to determine the dose of Veliparib to be used for the study.

5.1.1 Pharmaceutical Formulation

The chemical name of Veliparib is 1H-Benzimidazole-7-carboxamide,2-[(2R)-2-methyl-2-pyrrolidinyl]-, and its molecular weight is 244.29. Veliparib will be provided by AbbVie as immediate release capsules (strengths: 10, 20, 40, 50, and 100 mg). The components of the capsules are microcrystalline cellulose, colloidal silicon dioxide, magnesium stearate, gelatin, sodium lauryl sulfate, and titanium dioxide (may contain FD&C blue#1, FD&C yellow#6, or FD&C yellow#5).

5.1.2 Labeling and Packaging

Veliparib will be provided by AbbVie free of charge for this study. Veliparib will be packaged in bottles containing the capsules. Each bottle label will include all the information, as required by local regulations and must remain affixed to the bottle. The site staff must complete all blank spaces on the label prior to dispensing drug to the patient. AbbVie will provide the study site with detailed instructions and training for the handling of study supplies.

5.1.3 Dispensing Procedures and Storage Conditions

All clinical supplies provided by AbbVie must be stored in a secure place at the proper storage conditions until they are dispensed for patient use or are returned to AbbVie. Upon receipt of a shipment, the pharmacist will open and inspect the shipment, verify that the Veliparib has been

received intact/in the correct amounts/at the correct address, sign/date the proof of receipt, and register the shipment.

The investigational product is for investigational use only and is to be used only within the context of the study. Capsules must be stored in the original container at 15° to 25°C (59° to 77°F). Patients will receive enough capsules every 28 days (every cycle); patients must keep a diary indicating time and date of each dose. Patient diary will be reviewed by the study coordinator every 28 days and the diary will be kept within the study records at the end of the active therapy of the patient. Patients will be instructed to bring their used bottles of Lapatinib to each return visit, along with any unused tablets. The site will record the bottle number and dose of Veliparib given to each patient in the source documents.

Accountability for investigational clinical supplies at the site rests with the Investigator at the participating site. The investigational product will be shipped to a designated person at the study site and must be stored in a pharmacy, or other locked and secured in a storage facility, accessible only to those individuals authorized by the site's Principal Investigator. The study product will be administered in accordance with the protocol, only to patients participating in the clinical trial. It is a violation of the regulations to use unapproved study products for purposes other than those described in the protocol.

The site will complete the required documentation, provided by UAB to account for investigational product dispensation. Each time the study product is dispensed to a patient; all information must be recorded immediately on a drug dispensation form(s).

Unused capsules will be destroyed on site at the conclusion of the study and suitably documented by the study team. Empty bottles and partially used bottles with capsules should be recorded and destroyed as per institutional SOP's after study drug administration. All returns of study product will be accurately recorded on the provided form(s).

5.1.4 Adverse Events Associated With Veliparib

At present, there have been more than 800 patients exposed to ABT-888, however only one study tested this drug as a single agent. From this single agent study, conducted in subjects with cancer, the most common reported side effects ($\geq 10\%$) with veliparib as a single agent were: nausea (50), fatigue (43), anemia (32), hyperglycemia (27), lymphopenia (24), hypoalbuminemia (22), abdominal pain (22), diarrhea (22), decreased appetite (22), headache (20), low sodium (19), increases in liver enzymes (17), back pain (15), ascites (15), constipation (15), thrombocytopenia (12), leukopenia (12), dizziness (12), increased creatinine (10), dyspnea (12), insomnia (10), and dry mouth (10), hot flushes (10). Less frequent, but potentially severe events include dehydration (6.9). Based upon events of seizures in preclinical studies using high doses (much higher of what it will be used in this study) seizures are a potential risk; however, in ongoing clinical studies, uncommon events of seizure have been observed. In preclinical studies also it has been demonstrated that Veliparib absorbs ultraviolet light; therefore, the potential exists that Veliparib may contribute to a risk of reddening or tanning of the skin when exposed to direct sunlight. In addition, as with any drug, allergic reactions are a possibility from a simple rash to anaphylactic shock. Side effects on an unborn or nursing infant are not known; however, in preclinical studies harmful effects on fetal development have been noted in experimental pregnant animals.

5.1.5 Veliparib Dosing

The daily dose of Veliparib will be 200 mg PO every 12 hours continuously for 28 days (a cycle), starting on Day 2 Cycle 1. Patients developing grade 1 and 2 toxicities will be permitted to take a drug holiday of up to 14 days; after the drug holiday, if the adverse event has resolved to the satisfaction of the investigator, the study drug may be resumed at the same level. In the event of recurrent toxicity, there will be two dose reductions permitted (Veliparib 150 mg PO every 12 hours continuously and Veliparib 100 mg PO every 12 hours continuously). If the adverse event recurs, the patient will be taken off the study. Patients developing grade 3 and 4 toxicities will be interrupted for permitted for up to 14 days; after the drug holiday, if the adverse event has resolved to the satisfaction of the investigator, the study drugs may be resumed at a reduced dose (Veliparib 150 mg PO every 12 hours continuously). If the adverse event recurs, the patient will be taken off the study. **Veliparib will start on day 2.**

5.2 Lapatinib (GW572016 or Tykerb[®]) (See also Lapatinib Package Insert)

Lapatinib is an orally active dual HER1/HER2 kinase inhibitor that blocks signal transduction pathways. This dual inhibition is an attractive therapeutic strategy for epithelial cancers, as ligand-induced HER1/HER2 dimerization triggers off potent proliferative and survival signals. Lapatinib will be provided free of charge by Novartis Pharmaceuticals Corporation for this pilot study.

5.2.1 Packaging, Labeling, and Storage of Study Drug

Lapatinib will be supplied by Novartis Pharmaceuticals Corporation as lapatinib ditosylate monohydrate tablets. The tablets contain 250 of the active drug, and they are oval, biconvex, orange, film-coated, and are debossed on one side with FL HLS. The tablets contain 400 mg of lapatinib ditosylate monohydrate, equivalent to 250 mg lapatinib free base per tablet. Lapatinib must be stored at room temperature, in accordance with manufacturer guidelines.

All clinical supplies provided by Novartis Pharmaceuticals Corporation must be stored in a secure place at the proper storage conditions until they are dispensed for patient use or are returned to them. Upon receipt of a shipment, the pharmacist will open and inspect the shipment, verify that the lapatinib has been received intact/in the correct amounts/at the correct address, sign/date the proof of receipt, and register the shipment.

The investigational product is for investigational use only and is to be used only within the context of the study. Capsules must be stored in the original container at 15° to 25°C (59° to 77°F). Patients will receive enough capsules every 28 days (every cycle); patients must keep a diary indicating time and date of each dose. Patient diary will be reviewed by the study coordinator every 28 days and the diary will be kept within the study records at the end of the active therapy of the patient. The site will record the package number and dose of Lapatinib given to each patient in the source documents.

Accountability for investigational clinical supplies at the site rests with the Investigator at each participating site. The investigational product will be shipped to a designated person at the study site and must be stored in a pharmacy, or other locked and secured in a storage facility, accessible only to those individuals authorized by the site's Principal Investigator. The study product will be administered in accordance with the protocol, only to patients participating in the clinical trial. It is a violation of the regulations to use unapproved study products for purposes other than those described in the protocol.

The site will complete the required documentation, provided by UAB to account for investigational product dispensation. Each time the study product is dispensed to a patient; all information must be recorded immediately on a drug dispensation form(s).

Unused capsules will be destroyed on site at the conclusion of the study and suitably documented by the study team. Empty bottles and partially used bottles with capsules should be recorded and destroyed as per institutional SOP's after study drug administration. All returns of study product will be accurately recorded on the provided form(s).

5.2.2 Adverse Events Associated With Lapatinib

Expected non-hematologic toxicities for the use of Lapatinib include diarrhea, rash, mucositis, dry skin, elevation of the liver enzymes (especially in patients with prolonged use) and nausea. The majority of these events have been grade 1 and 2 and very rarely grade 3 or 4. Hematological toxicity has not been associated with this agent.

Diarrhea, including severe diarrhea, has been reported during treatment with Lapatinib. Diarrhea generally occurs early during treatment, with almost half of those patients with diarrhea first experiencing it within 6 days. This usually lasts 4 to 5 days. Lapatinib-induced diarrhea is usually low-grade, with severe diarrhea of NCI CTCAE Grades 3 and 4 occurring in <10% and <1% of patients, respectively. Early identification and intervention is critical for the optimal management of diarrhea. Patients should be instructed to report any change in bowel patterns immediately. Prompt treatment of diarrhea with anti-diarrheal agents (such as loperamide) after the first unformed stool is recommended. Severe cases of diarrhea may require administration of oral or intravenous electrolytes and fluids, use of antibiotics such as fluoroquinolones (especially if diarrhea is persistent beyond 24 hours, there is fever, or Grade 3 or 4 neutropenia), and interruption or discontinuation of therapy (see Appendix I for diarrhea management guidelines).

Lapatinib has been reported to decrease LVEF; in clinical trials, the majority (>57%) of LVEF decreases occurred within the first 12 weeks of treatment; however, data on long-term exposure are limited. Caution should be taken if Lapatinib is to be administered to patients with conditions that could impair left ventricular function. LVEF should be evaluated in all patients prior to initiation of treatment to ensure that the patient has a baseline LVEF that is within the institution's normal limits. LVEF should continue to be evaluated during treatment with Lapatinib to ensure that LVEF does not decline below the institution's normal limits.

Hepatotoxicity (ALT or AST >3 times the upper limit of normal and total bilirubin >2 times the upper limit of normal) has been observed in clinical trials (<1% of patients) and post-marketing experience. The hepatotoxicity may be severe and deaths have been reported. Causality of the deaths is uncertain. The hepatotoxicity may occur days to several months after initiation of treatment. Liver function tests (transaminases, bilirubin, and alkaline phosphatase) should be monitored before initiation of treatment, every 4 to 6 weeks during treatment, and as clinically indicated. If changes in liver function are severe, therapy with lapatinib should be discontinued and patients should not be retreated.

No pulmonary toxicity has been noted with lapatinib. However, interstitial lung disease (ILD) has been described in mainly lung cancer patients receiving tyrosine kinase inhibitors against HER1, like gefitinib. Interstitial lung disease, which may be acute in onset, has been observed uncommonly in patients treated with gefitinib. These patients usually present with a fairly acute onset of dyspnea,

sometimes associated with cough or low-grade fever. This may become quite severe within a short period of time and usually results in hospitalization. Radiological investigations, often including CT scan, frequently show pulmonary infiltrates or interstitial shadowing with ground-glass appearance. There is often respiratory distress with arterial oxygen desaturation. Cultures are frequently negative for bacterial growth. If patients present with an acute worsening of respiratory symptoms such as dyspnea, cough, and fever, lapatinib will be interrupted and the patient promptly investigated for ILD. If ILD is confirmed, lapatinib will be discontinued and the patient treated appropriately.

QT prolongation was observed in an uncontrolled, open-label dose escalation study of lapatinib in advanced cancer patients. Lapatinib should be administered with caution to patients who have or may develop prolongation of QTc. These conditions include patients with hypokalemia or hypomagnesemia, with congenital long QT syndrome, patients taking anti-arrhythmic medicines or other medicinal products that lead to QT prolongation, and cumulative high-dose anthracycline therapy. Hypocalcemia, hypokalemia, and hypomagnesemia should be corrected prior to lapatinib administration.

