3.0 STUDY DESIGN (Table 1 and Figure 7)

The study is an open-label, single arm, single institution, pilot clinical trial of Veliparib (a PARP inhibitor) in combination with Lapatinib (an EGFR inhibitor) in patients with pathologically confirmed TNBC (ER negative, PR negative, HER-2-Neu negative by IHC [0, 1] or FISH) who have not received prior therapy in the metastatic setting (but failed anthracyclines and taxanes in the

neoadjuvant or adjuvant setting) or who have failed prior chemotherapy in the metastatic setting (including anthracyclines and taxanes and no more than two prior regimens for metastatic disease as long as patients have adequate performance status – see Appendix B). The data obtained in this pilot study will be used to design a phase II clinical trial that will be conducted by the Translation Breast Cancer Research Consortium.

As described in **Figure 7**, patients will receive Lapatinib (1250 mg PO daily continuously) in combination with Veliparib (200 mg PO every 12 hours continuously). A cycle of therapy is defined as 28 days of PO therapy. Lapatinib will start Day 1 cycle 1 and Veliparib will start on Day 2 Cycle 1 (for better understanding of the PK of the drugs as well as to induce a DSB repair defect first with Lapatinib). Dose reductions of Lapatinib and Veliparib will be allowed. Patients developing grade 1 and 2 toxicities will be permitted to take a drug holiday of up to 14 days; after the drug holiday, if the adverse event has resolved to the satisfaction of the investigator, the study drugs may be resumed at the same level. In the event of recurrent toxicity, there will be two dose reductions permitted (dose reduction minus one will be Lapatinib 1000 mg PO daily continuously and Veliparib 150 mg PO every 12 hours continuously); dose reduction minus two will be Lapatinib 750 mg PO daily and Veliparib 100 mg PO every 12 hours continuously. If the adverse event recurs after dose reduction two, the patient will be taken off the study. Patients developing grade 3 and 4 toxicities will be interrupted for up to 14 days; after the drug holiday, if the adverse event has resolved to the satisfaction of the investigator, the study drugs may be resumed at a reduced dose (Lapatinib 1000 mg PO daily continuously and Veliparib 150 mg PO every 12 hours continuously). If the adverse event recurs, the patient will be taken off the study.

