5.2.3 Lapatinib Dosing

The daily dose of Lapatinib will be 1250 mg PO every 24 hours continuously for 28 days (a cycle). Patients developing grade 1 and 2 toxicities will be permitted to take a drug holiday of up to 14 days; after the drug holiday, if the adverse event has resolved to the satisfaction of the investigator, the study drug may be resumed at the same level. In the event of recurrent toxicity, there will be two dose reductions permitted (Lapatinib 1000 mg PO every 24 hours continuously and Lapatinib 750 mg PO daily). If the adverse event recurs, the patient will be taken off the study. Patients developing grade 3 and 4 toxicities will be permitted to take a drug holiday of up to 14 days; after the drug holiday, if the adverse event has resolved to the satisfaction of the investigator, the study drugs may be resumed at a reduced dose (Lapatinib 1000 mg PO every 12 hours continuously). If the adverse event recurs, the patient will be taken off the study. Lapatinib will start on day 1.

Patients should be carefully instructed by study personnel on how to take lapatinib. Patients will be instructed to take lapatinib, 1250 mg (5 tablets) PO on a daily basis, at approximately the same time each day. Lapatinib must be taken on an empty stomach—either 1 hour (or more) before a meal or 1 hour (or more) after a meal. Patients may not use anything but water to help them swallow their lapatinib. Medications that modify gastric pH, while not prohibited, are restricted and further described in the table of prohibited medications. Histamine H₂ antagonists and proton pump inhibitors are allowed. NOTE: Lapatinib is not to be taken with grapefruit or grapefruit juice. Grapefruit and grapefruit juice should not be taken at any time during the study. If the patient vomits after their lapatinib dose, the patient should be instructed not to retake the dose. Patients should take the next regularly scheduled dose of lapatinib. If vomiting persists, the patient should contact their study doctor.

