Patients who have a $\geq 20\%$ decrease in left ventricular cardiac ejection fraction relative to baseline, and the ejection fraction is below the institution's lower limit of normal, should have a repeat evaluation of ejection fraction 1-2 weeks later while still receiving investigational product. If the repeat ejection fraction evaluation confirms a $\geq 20\%$ decrease in left ventricular cardiac ejection fraction, and the ejection fraction is below the institution's lower limit of normal, then lapatinib should be temporarily discontinued. If the left ventricular ejection fraction recovers during the next 3 weeks, the patient may be restarted on investigational product at a reduced dose. For such patients, monitoring of left ventricular ejection fraction will then be performed 2 weeks and 4 weeks after rechallenge, and then every 4 weeks thereafter. If repeat ejection fraction evaluation still shows a decrease $\geq 20\%$ in left ventricular ejection fraction relative to baseline, and the value is below the institution's lower limit of normal, then the subject should be withdrawn from investigational product. Patients with an NCI CTCAE grade 3 or 4 LVEF relative decrease must be withdrawn from study medications. Patients will be monitored closely for pulmonary toxicity. Patients with an NCI CTCAE Grade 3 or 4 interstitial pneumonitis must be withdrawn from study medications.

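### Section 5.2.2 bars lapatinib retreatment after severe liver-function changes, but the general grade 3-4 rule permits resumption with no hepatic exception, and no precedence is stated

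*Combined protocol and SAP*

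**What the plan says.** **The hepatic rule.** Section 5.2.2 says: "If changes in liver function are severe, therapy with lapatinib should be discontinued and patients should not be retreated." It makes no allowance for recovery and gives no grade or laboratory limit for *severe*. The same paragraph describes hepatotoxicity as ALT or AST above 3 times the upper limit of normal (ULN) together with total bilirubin above 2 times ULN, and puts it at under 1% of patients in clinical trials. It says the event can be severe and that deaths have occurred, with causality uncertain.

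**The general grade 3-4 rule.** Section 3.0 says "Patients developing grade 3 and 4 toxicities will be interrupted for up to 14 days"; once the investigator is satisfied that the event has resolved, "the study drugs may be resumed at a reduced dose (Lapatinib 1000 mg PO daily continuously" with a matching veliparib reduction. Section 5.2.3 says "Patients developing grade 3 and 4 toxicities will be permitted to take a drug holiday of up to 14 days", after which "the study drugs may be resumed at a reduced dose (Lapatinib 1000 mg PO every 12 hours continuously". Section 5.1.5 has the same rule for veliparib: "the study drugs may be resumed at a reduced dose (Veliparib 150 mg PO every 12 hours continuously". None of the three excepts the liver or refers to 5.2.2.

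**The named overrides.** Section 6.2.3 says "Patients with an NCI CTCAE Grade 3 or 4 interstitial pneumonitis must be withdrawn from study medications" and has a parallel sentence for grade 3-4 LVEF decrease. Footnotes 8 and 10 of the 6.6 schedule repeat both. Neither place names the liver.

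**Related text.** Section 9.1.2 makes ALT of at least 3 times ULN, with either total bilirubin of at least 2 times ULN or INR above 1.5, reportable as an SAE. It attaches no treatment consequence. Section 4.3 does not allow a patient with unacceptable toxicity to one agent to continue on the other alone.

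**The concern.** Two sections answer the same question differently: may a patient whose severe liver event has settled receive lapatinib again? The dosing sections allow it at the investigator's judgement, while the drug-information section says no. The protocol does put organ-specific overrides in its treatment plan, so someone working from 3.0, 5.2.3, 6.2.3 or the schedule would meet the LVEF and pneumonitis bars but not the hepatic one.

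Safety is the primary objective, and the protocol itself reports deaths in connection with this toxicity. The rule followed also decides whether the patient stays on the combination. Under the general rule both drugs may restart at lower doses. Under 5.2.2 lapatinib ends, and 4.3 would then end veliparib too if the event counts as unacceptable toxicity.

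**Working it through.** The plan gives no figure to reproduce on this point. The check is mainly textual, with one short calculation.

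**1. The rules side by side**

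| Place | Trigger | Consequence | Liver named? |
|---|---|---|---|
| 3.0, 5.1.5, 5.2.3 | Any grade 3-4 toxicity | Interrupt up to 14 days; may resume if resolved | No |
| 5.2.2 | Severe liver-function change | Stop lapatinib; no retreatment | Yes |
| 6.2.3, 6.6 footnotes | Grade 3-4 LVEF decrease or interstitial pneumonitis | Must withdraw | No |
| 9.1.2 | ALT with bilirubin or INR elevation | Report as SAE | Yes, reporting only |

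**2. Trace one patient.** Take a grade 3-4 hepatic event that resolves within 14 days. Under 3.0 and 5.2.3, resumption is permitted. Under 5.2.2, it is barred if the event is severe. No sentence ranks the two.

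**3. How far the rules overlap depends on *severe*.**
- If it means grade 3-4, every such event falls under both rules. The only support is by analogy: 5.2.2 uses the word that way for another organ ("severe diarrhea of NCI CTCAE Grades 3 and 4 occurring in <10% and <1% of patients, respectively").
- If it means the combined ALT/AST-bilirubin event of 5.2.2, or a subset of it, an isolated transaminase rise need not conflict. A combined event graded 3-4 still would.
- If it is left to judgement, the overlap cannot be fixed in advance.

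The CTCAE limits for liver tests are not reproduced in the documents, so I do not map the laboratory criteria to grades.

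**4. How often.** Inputs: n = 20 (Section 7.4) and an assumed per-patient probability p. The documents give no p for the combination. For lapatinib they give under 1% for the combined event, and they describe its expected toxicities, liver-enzyme elevation included, as very rarely grade 3 or 4. Formula: P(at least one) = 1 − (1 − p)^20.

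- p = 1%: 1 − 0.99^20 = 0.18
- p = 2%: 1 − 0.98^20 = 0.33
- p = 5%: 1 − 0.95^20 = 0.64

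For each p this is an upper bound on the conflict, which needs the event also to resolve within 14 days and to count as severe. If only half of events at p = 1% did so, the effective rate would be 0.5% and P = 1 − 0.995^20 = 0.10.

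**5. Effect on the endpoints.** The toxicity definitions in 3.0, 7.1 and 7.6 count grade 3-4 non-hematologic toxicity, and none of their exceptions is hepatic. A drug-related event therefore counts once, for the endpoint and the stopping rule, whether or not treatment restarts. The ORR denominator is the ITT population (7.5), so it does not move. What can change is that patient's later exposure, response and PFS. On ORR, one patient is worth at most 1/20 = 5 percentage points.

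**6. A neighbouring inconsistency.** The reduced dose in 5.2.3 is written as 1000 mg every 12 hours, which is 2 × 1000 = 2000 mg a day. The starting dose is 1250 mg a day, and 3.0 gives 1000 mg daily for the same step. These passages also need reconciling. I take no position on which is right.

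**The case against.** The best defence is that the rules can be obeyed together. Resumption is permitted, never required, and depends on the investigator's satisfaction, so declining to restart breaches nothing in 3.0, 5.1.5 or 5.2.3. A specific hepatic rule can be read as narrowing a general permission. Section 4.3 (unacceptable toxicity) and Section 6.4 (persistent grade 3-4 events) give further grounds for stopping.

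Much of this stands. A reader might infer that the protocol orders rechallenge and forbids it for the same patient; the permissive wording does not support that. A reader might also picture sites following different rules, but this is a single-institution trial, so any divergence would be between physicians or between patients.

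The defence does not close the gap. The protocol never says that 5.2.2 prevails. It states its other overrides in 6.2.3 as mandatory and leaves the liver out, while the hepatic sentence sits in drug information and is worded as *should*. The general stopping grounds leave the decision to judgement, and 5.2.2 appears to remove that judgement.

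On frequency, a reader might infer a high rate from the 17 listed for liver-enzyme increases on single-agent veliparib (5.1.4), or from entry being allowed with AST/ALT up to 5 times ULN in patients with liver metastases. The first figure is not broken down by grade and belongs to the other drug. The second is an eligibility limit. Neither gives a grade 3-4 rate for the combination.

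**Conclusion.** The concern holds as an unreconciled permission and prohibition. A resolved grade 3-4 hepatic event may be rechallenged under 3.0, 5.1.5 and 5.2.3 and, if it counts as severe, may not be under 5.2.2. Precedence is unstated and *severe* is undefined for the liver.

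Its size is uncertain and could be small: at most 18%, 33% or 64% for at least one case in 20 if the event rate is 1%, 2% or 5%. All three rates are assumptions; only the under-1% lapatinib figure comes from the documents. The case for correction rests on the seriousness of the toxicity more than on its frequency.

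A reader might go further and infer that the toxicity estimate or stopping rule is compromised. The documents do not support that, because a drug-related grade 3-4 event is counted under either rule. The consequence is patient safety and continuation on the combination, with a limited effect on that patient's tolerance and efficacy data. This should be corrected, but it does not undermine the design.

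**What to change.** Reconcile 5.2.2 with 3.0, 5.1.5, 5.2.3, 6.2.3 and the 6.6 footnotes, so that one rule on retreatment after hepatic toxicity appears in all of them. Either list the liver among the named exceptions to the grade 3-4 resumption rule, or amend 5.2.2. The investigator and drug suppliers should decide which.

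State what *severe* means for liver changes. Two laboratory criteria are already in the protocol, in 5.2.2 and 9.1.2. They are not identical (ALT or AST against ALT only; above against at or above the limits), so the text should say whether either one applies. It should also say how the criterion works for patients with liver metastases, who may enter with AST/ALT already above 3 times ULN.

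The cost is a sentence or cross-reference in each section and one footnote, made through a protocol amendment. A metabolic panel is already drawn on day 1 of each cycle. The 9.1.2 criterion would also need bilirubin fractionation or INR, neither of which is in the 6.6 schedule, so choosing it could add tests when liver values rise. Depending on the rule chosen, a few patients may not be restarted.
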